Anastomotic Leakage in Colorectal Cancer Surgery in Syria: Risk Factors and Improvements Following Guideline Implementation – A Retrospective Cohort Study

November/16/2025

NCT07092631

**Study Protocol: Follow-Up Cohort on Anastomotic Leakage in
Colorectal Cancer Surgery at Damascus Hospital, Syria**

Study Title:

Official Title:

Anastomotic Leakage in Colorectal Cancer Surgery in Syria: A Retrospective Cohort
Study Before and After Guideline Implementation

Brief Title:

Anastomotic Leakage in Colorectal Cancer Surgery, Syria

Study Design:

- Type: Observational, Retrospective Cohort Study
- Number of Cohorts: Two sequential cohorts
- The first cohort: Pre-guideline cohort (January 2016 – March 2024)
- The follow-up cohort: Post-guideline follow-up cohort (April 2024 – October 2025)
- Study Phase: N/A (observational)
- Number of Participants: 19 (follow-up cohort)

Study Objectives:

- Primary Objective:

1. To evaluate the incidence of anastomotic leakage (AL) after implementation of updated institutional guidelines for colorectal cancer surgery.
- Secondary Objectives:
 1. To assess postoperative complications, perioperative blood transfusions, ICU admissions, and postoperative mortality in the follow-up cohort.
 2. To compare outcomes with the pre-guideline cohort to determine the impact of guideline implementation.
 3. To evaluate the effectiveness of perioperative interventions targeting modifiable risk factors (e.g., hypoalbuminemia, transfusions, steroid use)

Study Setting:

Department of General Surgery, Damascus Hospital, Syria.

Resource-limited, conflict-affected environment with predominantly open surgery; laparoscopic surgery available for selected patients.

Eligibility Criteria:

- Inclusion Criteria:

Patients who underwent elective resection of the sigmoid colon or rectum for histologically confirmed colorectal adenocarcinoma between April 2024 and October 2025.

Availability of complete medical records and laboratory data relevant to the study outcomes.

- Exclusion Criteria:

Emergency surgeries or non-elective resections.

Non-neoplastic (non-tumor) resections.

Incomplete or missing medical records.

Interventions / Exposure:

- No experimental interventions; retrospective observational study.
- Patients were managed under updated hospital guidelines, which included:

(Preoperative nutritional optimization) albumin ≥ 3.5 g/dL when possible

Reduced perioperative blood transfusions

Enhanced intraoperative safety protocols

Postoperative monitoring for high-risk patients

Outcome Measures:

- Primary Outcome:

Anastomotic leakage (AL), defined according to ISREC criteria: a defect in the intestinal wall at the colorectal or colo-anal anastomosis causing communication between intra- and extraluminal compartments. Confirmed clinically or radiologically.

- Secondary Outcomes:

Postoperative complications

ICU admission

Perioperative blood transfusions

Postoperative mortality

Data Collection:

Retrospective extraction from patient charts, operative notes, laboratory results, and radiology reports.

Structured follow-up telephone interviews where applicable.

Collected variables: demographics, lifestyle factors, comorbidities, tumor characteristics, surgical details, laboratory data, and postoperative outcomes.

Statistical Analysis:

Descriptive statistics for baseline characteristics.

Comparisons with pre-guideline cohort using Chi-square or Fisher's exact test for categorical variables; t-test or Mann-Whitney U test for continuous variables.

Statistical significance: $p < 0.05$.

Analysis performed using SPSS version 24.

Ethical Considerations:

Ethical approval obtained from the Institutional Review Board of the Syrian Private University (IRB No. 1497/436.)

Retrospective nature: waiver of informed consent obtained where applicable.

Patient confidentiality maintained via anonymization and secure data storage.

Timeline:

- Study Start Date January 2016 (original cohort)
- Follow-up Cohort Data Collection Start April 2024
- Follow-up Cohort Data Collection End October 2025
- Study Completion Date October 2025

Study Significance:

This follow-up cohort evaluates the real-world impact of evidence-based guideline modifications on anastomotic leakage and other postoperative outcomes in a resource-limited, war-affected setting. The findings will inform future clinical practice and risk-reduction strategies for colorectal surgery in similar low-resource contexts.

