## Background:

Anastomotic leakage (AL) is one of the most serious complications following colorectal surgery, associated with increased morbidity, mortality, prolonged hospital stays. It occurs when there is a disruption at the surgical connection between two segments of the bowel, most commonly involving the colon or rectum. Despite advances in surgical techniques and perioperative care, AL remains a persistent concern, particularly in colorectal cancer patients undergoing resection.

This study was conducted in Damascus, Syria—a country that has endured over a decade of armed conflict, leading to profound disruptions in the healthcare system. Hospitals in such settings face ongoing shortages of medical supplies and limited access to updated surgical technologies. Laparoscopic surgery is not routinely available, and open surgery continues to be the standard approach for most colorectal procedures, including elective cases. Given these challenges, there is a critical need for context-specific data to guide clinical decision-making and improve patient outcomes.

The present study aims to identify the risk factors associated with anastomotic leakage among colorectal cancer patients who underwent surgery in a resource-limited, conflict-affected setting. Understanding these factors can contribute to safer surgical practice and more informed perioperative management in similar environments worldwide.

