## **Study Design:**

- **Study Type:** Observational
- **Study Design:** Retrospective Cohort Study
- **Time Perspective:** Retrospective
- **Study Period:** January 2016 to February 2024
- **Data Source:** Patients medical records and surgical reports from Damascus Hospital.

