### **Statistical Analysis:**

All collected data was entered into a secure, password-protected database. Descriptive statistics were used to summarize patient demographics, tumor characteristics, and surgical variables. Categorical variables were presented as frequencies and percentages, while continuous variables were reported as means with standard deviations or medians with interquartile ranges, as appropriate.

Univariate analyses was performed to evaluate the association between each potential risk factor and the occurrence of anastomotic leakage within 30 days postoperatively.

Statistical analysis was conducted using SPSS software, version 26 (IBM Corp., Armonk, NY, USA). A p-value < 0.05 was considered statistically significant. Data validation and quality control procedures were applied throughout the analysis to ensure accuracy and consistency.

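### Objective 2 reads a pooled before/after difference as guideline impact, although the midpoints of the two periods lie about five years apart and calendar time is never examined

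*Protocol*

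**What the plan says.** The Protocol (Study Design) defines two sequential cohorts: "The first cohort: Pre-guideline cohort (January 2016 – March 2024" and "The follow-up cohort: Post-guideline follow-up cohort (April 2024 – October 2025". The combined protocol and SAP (Study Design) ends the first period one month sooner: "January 2016 to February 2024". The cohorts hold 100 patients (combined document, Sample Size) and 19 patients (Protocol, Study Design).

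Secondary Objective 2 of the Protocol is "To compare outcomes with the pre-guideline cohort to determine the impact of guideline implementation", and its Study Significance section also describes the study as evaluating the guideline's impact. The analysis behind this, in the Protocol's Statistical Analysis section, is "Comparisons with pre-guideline cohort using Chi-square or Fisher's exact test for categorical variables", with a t-test or Mann-Whitney test for continuous variables. For the first cohort, the combined document states: "Univariate analyses was performed to evaluate the association between each potential risk factor".

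Neither document plans a breakdown by year or period, a term for calendar time, a comparator restricted to recent years, or a concurrent control. Date of surgery is not among the listed variables. The Limitations section of the combined document names only the lack of a laparoscopic comparison group.

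**The concern.** A before/after difference equals the guideline effect only if, without the guideline, the later rate would have matched the pooled earlier rate. Here the earlier rate averages more than eight years of surgery in "a country that has endured over a decade of armed conflict, leading to profound disruptions in the healthcare system". That setting does not show that leak rates changed, but it makes a flat rate an assumption that needs checking, and the plan does not check it. Adjusting for patient characteristics would not remove a trend in supplies, staffing or technique.

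What is at stake is the meaning of Objective 2. Following the plan exactly, any trend that was under way before April 2024 enters the estimate and is described as guideline impact. The bias can go either way.

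**Working it through.** The documents state no leak rate, effect size or power, so there is no planned figure to reproduce. The check covers how much drift the design absorbs and what that does to the estimate and the test.

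**Inputs from the documents**
- Pre-guideline window: 99 months (8.25 years) by the Protocol, 98 months (8.17 years) by the combined document.
- Follow-up window: April 2024 to October 2025, 19 months.
- Patients: 100 and 19. Significance level 0.05, taken as two-sided because the documents do not say.

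**Assumptions:** operations evenly spread within each window; all leak rates below are illustrative.

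**1. Distance between the periods.** Count months from January 2016. The follow-up window runs from 99 to 118, midpoint 108.5.
- 99-month baseline: midpoint 49.5, gap 108.5 − 49.5 = 59 months = 4.92 years.
- 98-month baseline: midpoint 49, gap 108.5 − 49 = 59.5 months = 4.96 years.

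**2. Bias per unit of drift.** For a linear trend with no guideline effect, the spurious difference is yearly drift × gap. At 1 point per year this is 4.9 to 5.0 points, with the sign of the drift.

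**3. Worked example (98-month baseline, no guideline effect).**
- Falling from 20% to 10%: pooled mean 15%; expected follow-up rate 20 − 10 × 108.5/98 = 8.9%; spurious fall 6.1 points.
- Rising from 10% to 20%: pooled mean 15%; expected follow-up rate 10 + 10 × 108.5/98 = 21.1%; spurious rise 6.1 points.

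**4. Effect on the test.** Exact rejection probability of Fisher's test, 100 against 19:
- Flat at 15%: 3.3%.
- Falling 20% to 10%: 3.0%.

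For other base rates and steeper drift, assume a logistic trend with a yearly odds ratio from 0.95 down to 0.80:

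| Mean pre-guideline rate | Spurious fall (points) | Fisher rejection |
|---|---|---|
| 10% | 2.1 to 6.8 | 1.1% down to 0.3% (2.5% if flat) |
| 20% | 3.8 to 12.8 | 3.7% up to 17.5% (3.5% if flat) |
| 30% | 5.1 to 18.0 | 4.2% up to 30.1% (3.3% if flat) |

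The estimate is biased throughout. The false-positive rate rises clearly only when drift is steep and the base rate is 20% or more.

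**5. A recent comparator.** The last 24 pre-guideline months have their midpoint at month 86 or 87, so the gap is 22.5 or 21.5 months (1.9 or 1.8 years), and 1 point per year leaves 1.8 to 1.9 points. The window holds about 24 × 100/99 = 24 patients. The cost in precision, at an assumed 15% in both groups (approximate 95% half-width):
- Pooled: 1.96 × √[0.15 × 0.85 × (1/100 + 1/19)] = 17.5 points.
- Recent: 1.96 × √[0.15 × 0.85 × (1/24 + 1/19)] = 21.5 points.

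**6. Can calendar blocks show stability?** Blocks for 2016–2018, 2019–2021 and 2022 to early 2024 hold about 37, 36 and 27 patients. Under the 20%-to-10% decline, the observed rates fall strictly across all three blocks 32% of the time, against 14% when the true rate is flat. The first block exceeds the last in 78% of cases, so even that looser sign is missed in 22%.

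**The case against.** The strongest reply is that drift is not documented. Both documents describe a conflict-affected setting, so the setting alone is not evidence of change between the periods. The laparoscopy wording does not settle it either. The combined document says "Laparoscopic surgery is not routinely available, and open surgery continues to be the standard approach for most colorectal procedures", while the Protocol's Study Setting describes mainly open surgery with laparoscopy for selected patients. The two statements are compatible, and the first cohort already records open or laparoscopic approach. This stands: the wording is at most a weak hint, and the point does not rest on it.

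A reader might infer that background improvement would be declared a significant guideline effect. The documents and the arithmetic do not support that as a general claim. With 19 follow-up patients, even zero leaks reaches p < 0.05 only if at least 19 of the 100 earlier patients leaked. What remains is bias of unknown sign, which a confidence interval from the pooled comparison would not reflect.

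A reader might also infer that a flat-looking pre-guideline series would justify crediting the guideline. It would not, because step 6 shows that the blocks are too small to establish stability.

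Two further points have force. The comparison is a secondary objective; the primary one is leak incidence after implementation. And operation dates may not be in the analysis file, since date of surgery is not a listed variable and the first cohort's data are anonymized. Neither removes the problem: Objective 2 is worded causally, and the charts and operative notes are named data sources.

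**Conclusion.** The point holds as a limit on what Objective 2 can conclude. The planned comparison cannot separate a guideline effect from a secular trend, and about 4.9 to 5.0 years of any such trend enters the estimate: roughly 5 points for each point per year, in either direction. This rests on even accrual within each period. The leak rates and drift used above are illustrations, because the documents supply none.

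The harm is a biased estimate and an unsupported causal conclusion. In the worked example it is not an excess of false-positive tests, although steep drift at a high base rate could produce one. Sampling error with 19 patients (about ±17.5 points at 15%) exceeds the example's 6.1-point bias, which is a further reason for modest wording. The February or March 2024 end date needs reconciling but does not affect the conclusion.

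**What to change.** In the Protocol's Statistical Analysis section and the related text:

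1. Report leaks over patients in the pre-guideline cohort by calendar block (for example 2016–2018, 2019–2021, 2022 to early 2024) beside the follow-up cohort, using operation dates from the charts and operative notes.
2. Beside the pooled comparison, give the difference with a confidence interval between the follow-up cohort and the last 24 pre-guideline months, labelled as a descriptive sensitivity comparison.
3. Reword Objective 2 and the Study Significance section, whatever the table shows, as a change between periods, and list secular trend as a limitation. Do not treat the absence of a visible trend across blocks as grounds for attributing the change to the guideline.

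The cost is one extra table, retrieval of operation dates if they were not kept, an imprecise recent comparison (about 24 against 19 patients), and a weaker stated conclusion. No new patients are needed, and the changes remain possible now that data collection has ended. A segmented time-series model is not proposed, because 19 follow-up patients could not support one.

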### **Sample Size:**

All eligible patients meeting the inclusion criteria within the defined period were included. The final sample size was 100 patients.

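### The plan claims to determine the guideline's impact, but its only between-cohort analysis is an unadjusted significance test on 19 follow-up patients, with no effect interval and a 30-day leak window stated for the first cohort only

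*Protocol*

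**What the plan says.** **The claim.** Protocol, Study Objectives, Secondary Objective 2: "To compare outcomes with the pre-guideline cohort to determine the impact of guideline implementation". Study Significance: "This follow-up cohort evaluates the real-world impact of evidence-based guideline modifications". Secondary Objective 3 also speaks of the effectiveness of perioperative measures aimed at albumin, transfusion and steroid use.

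**The analysis.** Protocol, Statistical Analysis: "Comparisons with pre-guideline cohort using Chi-square or" Fisher's test for categorical variables, and a t-test or Mann-Whitney test for continuous ones, at p < 0.05. Neither document plans an effect measure, an interval, adjustment, stratification or any handling of time trend. The combined protocol and SAP plans univariate analyses only.

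**The cohorts.** Protocol, Study Design: "Number of Participants: 19 (follow-up cohort"). The Protocol gives no size for the first cohort and ends it in March 2024. The combined protocol and SAP says, under Sample Size, "The final sample size was 100 patients", from a study period that ends in February 2024.

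**The outcome.** In the Protocol, leakage is "defined according to ISREC criteria", with no time window. In the combined protocol and SAP, Statistical Analysis refers to "occurrence of anastomotic leakage within 30 days postoperatively" and names no leak definition.

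**Follow-up.** Protocol, Timeline: "Follow-up Cohort Data Collection End October 2025". Eligible operations run to the same month.

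**The concern.** A before-and-after comparison can describe a difference between two periods. To call that difference the guideline's impact, one must rule out chance and other changes between the periods. The plan does little about either. With 19 follow-up patients, the test will usually be non-significant even if the guideline works well, and a bare p-value invites the reading that it had no effect. A significant result could equally come from a different mix of patients or from change over calendar time, since more than eight years are set against 19 months.

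A single leak can decide the test, so the way leaks are counted matters. One document states a 30-day window and the other states none; one names a definition and the other does not. Study Significance says the findings are meant to inform practice elsewhere, so an over-read p-value would have consequences.

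**Working it through.** Neither document has a power or precision calculation, so there is no planned figure to reproduce.

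**Inputs.** Follow-up n = 19 (Protocol). First cohort n = 100 (combined protocol and SAP; assumed to be the comparator). Alpha = 0.05 (Protocol; sidedness not stated, two-sided assumed). Leak counts and risks are not in the documents, so those below are assumptions, shown over a range.

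**1. What the test needs.** Two-sided Fisher sums the hypergeometric probabilities of all tables no more likely than the one observed.

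- 19/100 vs 0/19 (19 leaks among 119): P(0 in follow-up) = 0.0270. The equally or less likely upper tail (7 or more) is 0.0108 + 0.0022 + 0.0003 = 0.0133. p = 0.040.
- 19/100 vs 1/19 (20 leaks among 119): P(1) + P(0) + P(6 or more) = 0.1024 + 0.0218 + 0.0672. p = 0.19.

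One more follow-up leak therefore reverses the conclusion. The smallest first-cohort counts giving Fisher p < 0.05 in favour of follow-up are:

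| Follow-up leaks | First-cohort leaks needed | Fisher p |
|---|---|---|
| 0/19 | 19/100 | 0.040 |
| 1/19 | 27/100 | 0.042 |
| 2/19 | 36/100 | 0.032 |

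These are Fisher thresholds. The Protocol also allows Chi-square and gives no rule for choosing. For 33/100 vs 2/19, uncorrected Chi-square = 119 × (33×17 − 67×2)² / (100 × 19 × 35 × 84) = 3.88, p = 0.049, while Fisher gives 0.057. The smallest expected count there is 35 × 19/119 = 5.6, so Chi-square would be a usual choice. In that band the result depends on which test is picked.

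**2. Chance of a significant benefit.** Sum, over all a of 100 and b of 19, Bin(a; 100, p1) × Bin(b; 19, p2) for tables with a/100 > b/19 and Fisher p < 0.05.

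| Assumed first-cohort risk | Risk halved | All leaks removed |
|---|---|---|
| 10% | 0.2% | 0.5% |
| 15% | 3.8% | 16.3% |
| 20% | 10.2% | 63.8% |

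The last column can be checked directly: with no follow-up leaks it is P(19 or more leaks in 100).

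**3. What an interval would show.** Newcombe 95% interval for the risk difference d (follow-up minus first cohort), from the Wilson limits (l1, u1) of the first cohort and (l2, u2) of the follow-up cohort:

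lower = d − √[(p2 − l2)² + (u1 − p1)²]; upper = d + √[(u2 − p2)² + (p1 − l1)²].

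- 19/100 vs 0/19: Wilson limits 12.5% to 27.8% and 0% to 16.8%; d = −19.0 points, interval −27.8 to −1.0.
- 20/100 vs 1/19: Wilson limits 13.3% to 28.9% and 0.9% to 24.6%; d = −14.7, interval −24.6 to +5.8.
- 15/100 vs 1/19: d = −9.7, interval −19.1 to +10.5.
- 10/100 vs 1/19: d = −4.7, interval −13.3 to +15.1.

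The last three include both a sizeable benefit and some harm. The p-value alone hides that.

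**4. Case-mix.** Suppose leak risk is 20% for rectal and 5% for sigmoid resections, and the guideline does nothing. If the rectal share falls from 60% to 40%, the crude risk falls from 0.6×20 + 0.4×5 = 14.0% to 0.4×20 + 0.6×5 = 11.0%. An unadjusted test cannot tell this from a guideline effect.

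**5. The window.** Without a limit, a leak after day 30 would count in the follow-up cohort but not in the first, which works against the guideline. But 1 October 2025 + 30 days = 31 October 2025, so anyone operated on after 1 October has under 30 days before data collection ends. If collection stopped then, later leaks in those patients are missed, which works for the guideline.

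**The case against.** The strongest reply is that this is a secondary objective of a study openly labelled observational and retrospective. The sample is whoever was eligible, the Protocol is dated after data collection ended, and 19 patients cannot support adjustment. All of that stands. Power can no longer be changed, and the figures above justify a change of claim and reporting, not a larger study or a multivariable model. The Protocol also plans descriptive baseline statistics, and its tests are not confined to outcomes, so case-mix differences may become visible. That helps the reader but does not make the comparison causal. The official title is itself built on before and after the guideline, so the comparison will be read as a main result.

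Some stronger readings are tempting but not supported:

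- *That the two documents set conflicting leak windows.* One states a rule and the other is silent.
- *That the open window could only hide a benefit.* The October 2025 patients show that it can also go the other way.
- *That the cohorts were selected differently.* The Protocol adds histological confirmation and complete records, but both documents exclude emergency and non-tumour surgery, and the earlier one records the same two tumour sites. The gap may be one of wording.
- *That similar accrual (19/19 = 1.00 and 100/98 = 1.02 patients per month) shows the cohorts are alike.* Stricter criteria with higher volume would give the same rate. Accrual says nothing about case-mix.

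**Conclusion.** The point holds and should be acted on. The plan claims an effect of the guideline that its analysis cannot establish in either direction. If the risk were halved, a significant benefit would appear in at most about one study in ten for an assumed first-cohort risk of 10% to 20%. One follow-up leak can move p from 0.040 to 0.19. The wording of the claim, the unadjusted tests, the missing interval and the unequal statement of the outcome are all read directly from the documents. The sizes rest on three assumptions: that the comparator is the 100 patients of the earlier document (its end date differs by a month from the Protocol's), that tests are two-sided, and the leak risks and counts chosen for illustration.

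A reader might infer that the whole study fails. It does not: follow-up leak incidence, the primary objective, can be reported without the comparison, although it too needs a stated window.

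**What to change.** 1. Reword Secondary Objective 2 and Study Significance along the lines of *estimate the difference in outcomes associated with the post-guideline period*. Recast Secondary Objective 3 as a description of albumin, transfusion and steroid use by cohort, since no planned analysis could show effectiveness.
2. Apply the earlier document's 30-day leak window to both cohorts, and confirm 30-day status for patients operated on after 1 October 2025. Use one leak definition for both cohorts, or state the difference as a limitation. Confirm the comparator's size and end date, and that its patients meet the Protocol's eligibility criteria.
3. Report the leak risk difference with a named 95% interval beside the p-value, and state that non-significance is not evidence of no effect. Newcombe is one suitable choice, and at 19/100 vs 0/19 it agrees with Fisher. An exact unconditional interval is also defensible, but for the same counts it runs from about −28 to +3 points despite p = 0.040.
4. State case-mix and calendar-time confounding as limitations, and show the planned baseline characteristics by cohort.

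**Cost.** The changes are rewording, one interval, and a check of leak dates in at most 19 charts, because the earlier document already applies the window to the first cohort. Applying a single definition retrospectively could mean re-reading up to 100 charts, hence the option of a stated limitation. The claim becomes softer and the interval will be wide. Confounding by calendar time remains whatever is done.

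### Follow-up patients must have complete records and laboratory data to enter but no such rule is listed for the pre-guideline cohort, so the 19 may not represent all eligible resections after implementation, in an unknown direction

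*Protocol*

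**What the plan says.** The Protocol's primary objective is "To evaluate the incidence of anastomotic leakage (AL) after implementation of updated institutional guidelines for colorectal cancer surgery". Its Study Significance section describes the purpose more broadly: "This follow-up cohort evaluates the real-world impact of evidence-based guideline modifications on anastomotic leakage".

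Entry to the follow-up cohort is conditioned on completeness twice. The inclusion criteria require "Availability of complete medical records and laboratory data relevant to the study outcomes", and the exclusion criteria list "Incomplete or missing medical records". No minimum data set is named, so what counts as complete is left to whoever reads the chart. The cohort is given as "Number of Participants: 19 (follow-up cohort)".

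The Combined protocol and SAP covers January 2016 to February 2024 at the same hospital. Its inclusion and exclusion criteria remove only emergency and non-tumor operations. Its Sample Size section says that all eligible patients were taken, 100 in total. It lists no completeness condition. The Protocol's Statistical Analysis section then compares the two cohorts.

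**The concern.** The incidence the Protocol wants is that of eligible patients operated on after implementation. Whether a chart and its laboratory data are complete is settled partly during and after the patient's care, so the rule selects on information that can be related to how that care went. A record cut short by transfer or by readmission elsewhere could remove a patient with a poor outcome. A patient with a straightforward stay and few blood tests could be removed just as easily.

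The rule can also drop a patient whose leak status is known. The Protocol confirms leakage clinically or radiologically, so a missing laboratory value does not by itself stop the outcome being counted.

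The primary incidence is at stake. The secondary rates of complications, ICU admission, transfusion and death pass through the same filter. Because the rule is written for one cohort only, the before-after comparison is exposed as well.

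**Working it through.** **Inputs from the documents**
- Follow-up cohort: n = 19, April 2024 to October 2025, which is 9 + 10 = 19 months (Protocol, Study Design).
- Pre-guideline cohort: n = 100 (Combined protocol and SAP, Sample Size). The period is 98 months if it ends in February 2024 (Combined protocol and SAP) and 99 months if it ends in March 2024 (Protocol).
- Significance level 0.05 (both documents).

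**Assumptions, because the documents give no values**
- The number of leaks in either cohort, the number excluded for incompleteness, and the chance that a record is complete in patients with and without a leak.

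The plan gives no calculation behind the 19, so there is no figure of its own to reproduce.

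**1. Bounds on the incidence.** With x leaks among the 19 and k patients excluded, the incidence among all 19 + k lies between x/(19 + k), if no excluded patient leaked, and (x + k)/(19 + k), if all did.

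| Leaks seen | Excluded k | Lower | Upper |
|---|---|---|---|
| 1/19 = 5.3% | 2 | 1/21 = 4.8% | 3/21 = 14.3% |
| 1/19 | 3 | 1/22 = 4.5% | 4/22 = 18.2% |
| 1/19 | 5 | 1/24 = 4.2% | 6/24 = 25.0% |
| 0/19 = 0% | 2 | 0% | 2/21 = 9.5% |
| 0/19 | 5 | 0% | 5/24 = 20.8% |

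When 1/19 is seen, the lower bound is below 5.3%, so the reported figure could be too high as well as too low.

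**2. Direction.** Let p be the true leak rate, and r1 and r0 the proportions of leak and non-leak patients with complete records. The expected observed rate is p·r1 / [p·r1 + (1 − p)·r0]. With p = 15% assumed:
- r1 = 50%, r0 = 90%: 0.075 / (0.075 + 0.765) = 8.9%.
- r1 = r0 = 90%: 15.0%, no bias.
- r1 = 90%, r0 = 70%: 0.135 / (0.135 + 0.595) = 18.5%.

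**3. Effect on the comparison.** Two-sided Fisher's exact test, with the effect of restoring one excluded patient who leaked:

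| Assumed pre-guideline leaks | 0/19 | 1/20 |
|---|---|---|
| 15/100 | p = 0.125 | p = 0.305 |
| 20/100 | p = 0.040 | p = 0.193 |
| 25/100 | p = 0.012 | p = 0.071 |

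Under the last two assumptions, one chart moves the result across 0.05. Under the first it does not.

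**4. Any sign of exclusions?** Pre-guideline accrual was 100/98 = 1.02 patients per month (100/99 = 1.01), against 19/19 = 1.00 in the follow-up. The earlier rate would predict 19 × 1.01 to 19 × 1.02, that is 19.2 to 19.4 patients. The counts show no heavy exclusion. They cannot rule out one or two excluded patients, and surgical volume may have changed.

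**The case against.** The strongest reply is that the documents do not say that anyone was excluded for incompleteness. If nobody was, or if completeness is unrelated to leakage, the incidence is unbiased. Accrual fits that possibility. Even if a few were excluded, the exact 95% interval for 1/19 is already 0.1% to 26.0%, wider than the shifts shown above. Some record is also unavoidable in a chart review, because eligibility and a confirmed leak have to be established from something. All of this stands. It limits the point to a risk, and it argues against simply deleting every data requirement. It does not answer the missing exclusion count, or the use of the rule in one cohort only. Sampling uncertainty does not account for selection.

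The Protocol's telephone interviews could recover some outcomes. They are not linked to eligibility, so a recovered outcome does not restore an excluded patient.

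A reader might go further in two ways that the documents do not support.
- **Selection on adherence.** Because the guideline includes "albumin ≥ 3.5 g/dL when possible", one might infer that the rule keeps only patients managed as the guideline intends. The criterion does not name albumin, and it refers to laboratory data relevant to the outcomes, among which albumin is not listed. The third secondary objective mentions hypoalbuminemia, so a wider reading is arguable. Even then, a recorded albumin does not show compliance: a patient with a low value and no optimization has complete data and stays in.
- **A downward bias.** One might infer that the rule lowers the leak rate. Patients who leak or go to ICU may have fuller laboratory and radiology records, which would raise it.

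**Conclusion.** The concern holds as a selection risk that the plan neither controls nor reports. The completeness rule is in force for the follow-up cohort, has no counterpart in the Combined protocol and SAP, and can remove patients whose leak status is known. It may make the 19 unrepresentative of all eligible resections after implementation, and it may bias the comparison.

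The direction is not fixed and the amount is unknown, possibly zero. On an assumed 1/19, the incidence among all operated patients lies between 4.8% and 14.3% if 2 were excluded, and between 4.2% and 25.0% if 5 were. These figures rest on assumed counts of leaks and exclusions. They show how much one or two patients can matter at this sample size and do not estimate the bias. The difference between the cohorts lies in the written rules: the documents do not say whether pre-guideline patients with poor records were in practice left out.

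The change should be made, because it is cheap and removes a selection step that a simple incidence does not need.

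**What to change.** 1. Replace both completeness criteria with a minimum requirement that the record establishes eligibility: elective resection of the sigmoid colon or rectum, histologically confirmed adenocarcinoma, and an operation date in the window. Identify patients from operative records.
2. Keep in the primary incidence every such patient whose leak status can be found from any source, including the planned telephone interviews.
3. Treat missing laboratory values as missing covariates and report how many there are. Do not exclude patients for them.
4. For patients whose leak status stays unknown, give the number, and report the incidence with all counted as no leak and with all counted as leak.
5. Report the number of resections identified, the number excluded, and the reasons.
6. Apply the same rule to the pre-guideline cohort.

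The cost is some empty covariate cells, possible re-review of a few charts, and a range around the incidence if any outcome stays unknown. If nobody was excluded from the follow-up cohort for incompleteness, a sentence saying so settles that part. The rule for the pre-guideline cohort would still need to be stated.
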